### 11.8 Secondary Analyses on compliance on the outcome effects

We anticipate that not all participants will attend all five intervention sessions. To assess whether participants who attend more intervention sessions exhibit greater magnitudes of

behavior changes, in addition to the binary treatment indicator (control vs. REMAS) we will create a three-level attendance covariate (attended no sessions, attended one, two, or three sessions, or attended four or more sessions), as done similarly in the NIMH Multisite HIV Prevention Trial Group (1998). We will then include this attendance covariate and its interaction with the treatment indicator to the regression models proposed above to see whether there is a significant intervention by dose (number of sessions attended) interaction for our outcome variables.

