## **6.3 Administration of Study Therapies**

The control condition intervention will be delivered in a single session of approximately 60 minutes (see table 1). The experimental intervention, REMAS will be delivered in five group sessions of approximately 90 minutes each spread out over three consecutive weeks. The intervention will be manual driven (see table 2).

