Since all covariates used in the model are baseline covariates, we can assume we have complete information on the covariates. A patient who drops out during the study will result in missing outcomes. To be able to deal with possible missing-data, we will use the multiple imputation technique combined with the standard Generalized Estimating Equation (GEE) method for the parameters in model (1),  $\beta = (\beta_0, \beta_1, \beta_2, \beta_3, \beta_4)$ . A similar method for handling missing covariates has also been proposed by Xie and Paik (1997). In this multiple imputation approach, a missing value of the outcome will be imputed using a Bayesian bootstrap method (Rubin, 1987; Xie and Paik, 1997) to obtain 5 imputed values, resulting in 5 complete-data sets. We will use the following steps in this multiple imputation scheme: (1) we will build a logistic regression model to predict the missingness for the outcome; (2) based on this model we will assign a propensity score for missingness for each case; (3) for each patient with a missing outcome (Y), its donor pool of patients having observed outcomes will

be found such that their assigned propensity scores are close to the assigned propensity score for the patient with the missing outcome; (4) for the missing value of Y for the patient, we will generate 5 imputation values from its donor pool according to the Approximate Bayesian Method (Rubin, 1987).

This multiple imputation method has been implemented by Solas (Statistical Solutions Ltd, 2001). For each complete-data set, we will apply the standard GEE method to get a pair of GEE estimates for  $\beta$  and its variance, resulting in 5 pairs. Then, according to Rubin's formula (Rubin, 1987), we will obtain the multiple-imputation estimate for  $\beta$  and its variance with associated p-value and 95% confidence interval.

Although the above method can handle both missing at random (MAR) and non-MAR missing data patterns, the validity of the method requires appropriately modeling the missing-data mechanism. To assess sensitivity of the conclusions on the assumed missing-data mechanism we will use both a parametric model (Robins et al, 1994; Scharfstein et al, 1999) and a non-parametric model (Wang et al, 1997).

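### The intervention-by-dose test in section 11.8 crosses three attendance levels with arm, but controls have one session, so half of the interaction cannot be estimated and the rest is not a like-for-like dose comparison

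*Protocol*

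**What the plan says.** Section 11.8 starts from the expectation of incomplete attendance: "We anticipate that not all participants will attend all five intervention sessions". It defines an attendance variable with the levels "attended no sessions, attended one, two, or three sessions, or attended four or more sessions", added to the binary arm indicator. It continues: "We will then include this attendance covariate and its interaction with the treatment indicator to the regression models proposed above". The stated purpose is to look for a "significant intervention by dose (number of sessions attended) interaction for our outcome variables".

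The number of sessions on offer is fixed elsewhere. For control, section 6.3 states: "The control condition intervention will be delivered in a single session of approximately 60 minutes". For the experimental arm it states: "REMAS will be delivered in five group sessions of approximately 90 minutes each spread out over three consecutive weeks". Sections 4.0 and 6.1.1 agree that control is one session.

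The models being extended are those of sections 11.6 and 11.7: arm, time, arm by time, baseline frequency, non-monogamy and years of stimulant use. Of these covariates section 11.6 says: "Since all covariates used in the model are baseline covariates, we can assume we have complete information on the covariates". Section 11.8 does not restrict the analysis to REMAS, does not express attendance as a share of sessions offered, and names no predictor of attendance.

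**The concern.** An interaction between arm and attendance level needs men from both arms at each level. Here one arm cannot supply any men at the top level, whatever the sample size. At the two lower levels the same label describes different behaviour in the two arms. A control at level 1-3 has attended everything he was offered, while a REMAS man at that level has missed two to four sessions. A control at level 0 missed one sitting, while a REMAS man at that level missed five spread over three weeks.

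Attendance is also an outcome of the period after randomisation and is plausibly tied to prognosis. Section 5.6 bars men who leave or are discharged from drug treatment from further sessions but keeps them in follow-up, and section 5.6.2 lets staff withdraw a man from the groups. Low attendance in REMAS therefore partly marks leaving treatment, and a three-week course leaves more room for this than a single sitting.

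At stake is a pre-specified test, applied to the primary and the seven secondary outcomes, whose result would be read as evidence for or against a dose effect.

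**Working it through.** **1. Inputs.** Attendance levels 0, 1-3 and 4+ (section 11.8). Sessions offered: control 1, REMAS 5 (section 6.3). Section 11.8 states no figure, so there is none to reproduce.

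**2. Design over the cells that can occur.** Let T = 1 for REMAS, A1 = 1 for level 1-3 and A2 = 1 for level 4+. The linear predictor for this block is b0 + bT·T + a1·A1 + a2·A2 + d1·T·A1 + d2·T·A2.

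| Cell | 1 | T | A1 | A2 | T·A1 | T·A2 |
|---|---|---|---|---|---|---|
| Control, 0 | 1 | 0 | 0 | 0 | 0 | 0 |
| Control, 1-3 | 1 | 0 | 1 | 0 | 0 | 0 |
| REMAS, 0 | 1 | 1 | 0 | 0 | 0 | 0 |
| REMAS, 1-3 | 1 | 1 | 1 | 0 | 1 | 0 |
| REMAS, 4+ | 1 | 1 | 0 | 1 | 0 | 1 |

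The A2 and T·A2 columns are identical. A numerical check gives rank 5 for 6 parameters.

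**3. What can be estimated.**
- Yes: the arm effect at level 0 (bT); the arm effect at level 1-3 (bT + d1); the interaction term d1; REMAS 4+ versus 0 (a2 + d2); REMAS 4+ versus 1-3 (a2 + d2 - a1 - d1).
- No: a2 alone, d2 alone, and the arm effect at 4+ (bT + d2).

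The interaction nominally has 2 degrees of freedom (d1, d2). Only d1 remains.

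**4. What d1 is.** On the model scale, d1 = (REMAS 1-3 minus REMAS 0) minus (control 1-3 minus control 0). It is a difference in differences. The REMAS-control contrast at level 1-3 is a separate quantity, bT + d1.

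**5. Illustration of the selection problem.** None of these inputs is in the protocol: no true arm effect; a latent trait that raises attendance (75% per session at its mean, log-odds slope 1) and shifts the outcome (mean 20, log-rate slope 0, -0.25 or -0.5); no baseline adjustment and no clustering. Mean counts by cell:

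| Slope | Control 0 | Control 1-3 | REMAS 0 | REMAS 1-3 | REMAS 4+ |
|---|---|---|---|---|---|
| 0 | 20.02 | 20.01 | 19.90 | 19.98 | 20.03 |
| -0.25 | 23.85 | 19.33 | 31.67 | 23.80 | 18.12 |
| -0.5 | 30.02 | 19.73 | 51.48 | 29.60 | 16.99 |

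The intention-to-treat rate ratio is 1.00 in every row. The REMAS/control ratios within level are:
- slope 0: 0.99 (level 0) and 1.00 (level 1-3);
- slope -0.25: 1.33 and 1.23;
- slope -0.5: 1.72 and 1.50.

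Under the log link, exp(d1) is the ratio of the two within-level ratios. At slope -0.25 it is 1.2310/1.3279 = 0.93. At slope -0.5 it is 1.5004/1.7150 = 0.87. With no link between trait and outcome it is about 1.00. So the surviving term can depart from the null when neither intervention differs from the other.

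The within-REMAS gradient is exposed to the same selection: 4+ versus 1-3 gives 18.12/23.80 = 0.76 at slope -0.25 and 16.99/29.60 = 0.57 at slope -0.5, again with no true effect.

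**The case against.** The strongest reply is that this is a labelled secondary analysis with an associational question: whether men who attend more sessions change more. The five-cell model still answers that within REMAS, since 4+ versus 1-3 and 4+ versus 0 can both be estimated. This stands. A reader might infer that the whole compliance analysis is inestimable. It is not: what fails is the split of the 4+ effect into a main effect and an interaction, and with it the formal interaction test at that level.

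A second reply is that attendance could be scored 0, 1, 2 as a linear term, which removes the aliasing. It does so only by extrapolating the control slope to sessions that controls cannot attend. Section 11.8 does not specify such scoring, and the difference in meaning between arms would remain.

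A third is precedent, since section 11.8 says the approach resembles one used in the cited multisite trial. Section 1.1.2 describes that trial as one-hour education against seven sessions. The protocol does not show how its control arm was handled, and a citation does not fill an empty cell.

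Two further inferences are tempting. One is that the surviving coefficient compares fully compliant controls with poorly compliant REMAS men; step 4 shows that it is a different quantity, and level 1-3 includes men who attended 3 of 5. The other is that software will silently drop a term. The protocol names no program for this model (the one in section 11.6 is for imputation), and programs may equally warn or fail.

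Finally, self-selection limits any attendance analysis. That is so, but here it acts differently in the two arms, which a cross-arm interaction needs it not to do.

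**Conclusion.** The point holds in a limited form. By the protocol's own design the control-by-4+ cell is empty, the arm and attendance block has rank 5 for 6 parameters, and one of the two interaction degrees of freedom does not exist. This rests on treating attendance as the three-level factor that section 11.8 describes; no outside figure is needed. The remaining degree of freedom compares the 1-3 versus 0 contrast between arms. It is not a like-for-like dose comparison, because the levels mean different things in each arm and attendance follows randomisation.

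The simulated ratios show that a spurious signal is possible and how it could arise. They depend on assumed slopes, and adjustment for baseline frequency could reduce them. They do not predict this trial.

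A reader might infer that the trial's main conclusion is at risk. It is not: sections 5.7, 11.6 and 11.7 analyse all randomised men as assigned, and neither the sample size nor the interim rule uses attendance. Nor is this a detail left to an analysis plan, because the protocol itself fixes the variable, its levels and the interaction. It should be corrected, as a secondary-analysis defect.

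**What to change.** In section 11.8, delete the attendance-by-arm interaction test. Replace it with an estimate of the gradient by sessions attended in the REMAS arm only (4+ versus 1-3 and versus 0, or number of sessions), using the same baseline covariates and allowing for cohort clustering. State that it is observational and not a randomised comparison.

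The cost is revised wording and a re-specified model for each outcome that section 11.8 covers. The gradient uses about half the sample (roughly 280 of the planned 560) and supports no causal dose claim. Level 0 may be thin: under the attendance assumed above it holds 1.8% to 1.9% of REMAS men, or about 5 of 280, so 4+ versus 1-3 is likely to be the more stable contrast.

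An instrumental-variable analysis with randomised arm as the instrument could be added, but only as an optional sensitivity analysis. Control material is drawn from REMAS sessions 1 and 2 (section 6.1.1). A man who would attend no REMAS session might still attend the control session, so assignment could affect his outcome without any REMAS exposure, and the exclusion restriction is doubtful. Defining exposure as 4+ sessions strains it further, since men with 1-3 sessions would count as unexposed.

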### 11.9 Interim Analyses

Given the absence of strong evidence supporting the impact of this intervention, as suggested by a reviewer we will plan to conduct an interim analysis, primarily for futility. We will use the method of stochastic curtailment using the conditional power method (Lan and Wittes, 1988; Jennison and Turnbull, 1999). This approach will provide the statistical rationale for consideration of early termination. We will briefly describe this interim analysis technique as follows.

Let  $T$  be the test statistics we will be using for testing the primary null hypothesis for our primary outcome  $H_0: \beta_1=0$  versus  $H_1: \beta_1 >0$ . We will perform one interim analysis when 50% of the participants have finished the 3 month follow up. Let  $D(1)$  denote the data accumulated when we perform the interim analysis. The formal stopping rule at the interim analysis is given as follows. We will first compute the conditional power, which is defined as follows:

$$P(0)=P(T \text{ will reject } H_0 \text{ at the end of the study} \mid D(1), \beta_1 =0).$$

Then, if  $1-P(0) \geq 0.8$  we will recommend to terminate the study early due to futility. If  $1-P(0) < 0.8$ , we will recommend the study be continued. For a detailed discussion of this approach, see Chapter 10 of Jennison and Turnbull (1999).

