where  $\varepsilon_k = (\varepsilon_{11k}, \dots, \varepsilon_{I(2m)k})'$  has a multivariate normal distribution with mean zero and covariance matrix  $\sigma^2 R$ . Here the correlation matrix  $R$  contains 1 for its diagonal entries and  $\rho$  for off-diagonal entries. Here  $\sigma^2$  is the variance of  $\varepsilon_{ijk}$  and  $\rho$  represents the correlation between any two observations from the same cohort as well as the correlation between two observations from different cohorts within the same CTP site. Note that we assume that the correlation between two observations from the same cohort is the same as the one between two observations from different cohorts within the same CTP site. Under this linear model, to detect the effect size  $\Delta$  in the average number of unprotected vaginal and anal intercourse between the intervention and control conditions at the type I error  $\alpha$  with a power of  $1-\beta$ , we need the following number of cohorts per condition in the study:

$$m = 2(z_{1-\alpha/2} + z_{1-\beta})^2 \{1 + (I-1) * \rho\} / (I * (\Delta)^2),$$

where  $z_{1-\beta}$  is the  $(1-\beta)$ th percentile of the standard normal distribution. This formula is the same as Formula (5.1) in Donner and Klar (2000).

From the above formula, we see that to calculate a required sample size we need to determine the standardized effect size  $\Delta$ . We have estimated the effect size on the basis of clinically important intervention effects observed in prior studies. The NIMH Multisite HIV Prevention Trial Group (1998) used the number of unprotected vaginal and anal intercourse acts as a primary outcome measure in Project Light. They observed an effect size ( $\Delta$ ) of 0.29. Assuming that we have an intracluster correlation no greater than  $\rho$  of 0.01 and an average of 8 participants per cohort ( $I=8$ ), using the above formula we find that the number of cohorts per condition required to detect the effect size of 0.29 with a type I error rate of 0.05 and a power of 80% is:

$$m = 2 * (1.96 + 0.84)^2 * \{1 + (8-1) * 0.01\} / (8 * (0.29)^2) = 25,$$

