Therefore, we would require a total of  $8*25=200$  participants per condition, resulting in the total of 400 subjects in the study. Assuming each CTP site can contribute up to 40 subjects, the required number of CTP sites is 10. If each CTP site can only contribute an average of 32 subjects, we would require a total of 12 CTP sites. If each CPT can only contribute an average of 28, we would need a total of 14 CPT sites. Therefore, if we can recruit 14 good CTP sites, we would require each site to contribute a total of 28 subjects.

The following table provides estimates of the number of cohorts sites needed based on the above formula as should the average cohort size be less than 8.

I	# of the required cohorts per conditions
7	29
6	33
5	39
4	49

To allow a possible attrition rate of 10%, we would require a total of 440 participants for the estimate based on I=8. The investigators recognize that sample size calculations are best estimates based on previously obtained data when available. The effect size and intracluster correlation variation can result in significant variation in the sample sizes needed to obtain adequate power. For example if the intracluster correlation is twice what we are estimating (0.02) the total number of participants needed is 216 per condition or 476 total participants with 10% attrition rate. We propose to enroll 560 participants into the study. We feel this will provide some “cushion” for possible attrition, difficulty recruiting at any one site, or under estimation of the intracluster correlation.

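### The futility rule computes conditional power under zero effect, so it recommends stopping unless the interim result is already nearly significant, and cuts the planned 80% power to about 50%

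*Protocol*

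**What the plan says.** Protocol section 11.9 (Interim Analyses) describes stochastic curtailment by conditional power, mainly for futility. On timing it says: "We will perform one interim analysis when 50% of the participants have finished the 3 month follow up". The primary test is of beta1 = 0 against beta1 > 0. P(0) is defined as the probability that the test rejects at the end of the study, given the accumulated data and beta1 = 0. If 1 - P(0) is 0.8 or more, "we will recommend to terminate the study early due to futility"; otherwise the study is to continue. The section presents this as its formal stopping rule. It names no other effect for the calculation and no efficacy boundary.

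Section 11.3 (Sample Size and Statistical Power) sizes the trial to "detect the effect size of 0.29 with a type I error rate of 0.05 and a power of 80% is" 25 cohorts per condition. It takes an intracluster correlation "of 0.01 and an average of 8 participants per cohort", which gives 200 "participants per condition, resulting in the total of 400 subjects in the study". It then states: "To allow a possible attrition rate of 10%, we would require a total of 440 participants", and "We propose to enroll 560 participants into the study". It does not mention any power lost to the futility rule.

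**The concern.** A futility rule should identify trials that are unlikely to succeed even if the treatment works as hoped. The rule in section 11.9 instead assumes that all remaining data carry no treatment effect. Under that assumption, final significance is improbable unless the interim data have nearly secured it already. A low P(0) therefore does not mark a hopeless trial; it is what most successful trials would show halfway. Conditioning on the null suits the opposite decision, stopping because rejection is almost certain even with no further effect.

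If the rule is followed, a large share of trials in which REMAS works as planned would be stopped as futile. The 80% power in section 11.3 would then not describe the design, and an early stop cannot be undone.

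**Working it through.** **Inputs**
- Two-sided alpha 0.05 (1.96), power 80% (0.84), effect size 0.29, intracluster correlation 0.01, cohort size 8: section 11.3.
- Threshold: stop if 1 - P(0) >= 0.8, that is, P(0) <= 0.2: section 11.9.
- Information fraction t = 0.5: an assumption, from the look at 50% of participants. The range 0.4 to 0.6 is shown below.
- Z is oriented so that positive values favour REMAS.

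**The plan's own figure**

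m = 2 × (1.96 + 0.84)² × {1 + 7 × 0.01} / (8 × 0.29²) = 24.94, rounded up to 25 cohorts, or 200 per condition. This reproduces. The corresponding expected final Z (the drift) is 1.96 + 0.84 = 2.80.

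**Where the rule stops**

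On the B-value scale, with no effect in the remaining data:

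P(0) = Phi((Z_t × √t - 1.96) / √(1 - t))

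The trial continues only if P(0) > 0.2, that is, if

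Z_t > (1.96 - 0.842 × √(1 - t)) / √t

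At t = 0.5 this is (1.96 - 0.842 × 0.707) / 0.707 = 1.93, a two-sided p of about 0.054.

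**What that does under the planned effect**

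- The expected interim Z is 2.80 × 0.707 = 1.98. At that value P(0) is only 0.21, so a trial exactly on course barely escapes.
- P(stop) = Phi(1.93 - 1.98) = 48%.
- Overall power is P(Z_t > 1.93 and Z_final > 1.96), bivariate normal with correlation √t: 49.8%, against 80% without the rule. A simulation of 2,000,000 trials gave 47.9% stopping and 49.8% power.
- At the boundary Z = 1.93, conditional power is still 87% under the planned effect and 86% under the observed trend. The rule calls this trial futile.
- With no true effect, the trial stops 97.3% of the time.

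**Other settings**

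For 560 enrolled and 10% attrition, 252 per condition are analysed. With a mean cohort of 40/6 = 6.67, the design effect is 1 + 5.67 × 0.01 = 1.057 and the drift is 0.29 / √(2 × 1.057 / 252) = 3.17.

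| Setting | t | Continue if Z > | Stop, effect true | Power without rule | Power with rule |
|---|---|---|---|---|---|
| Planned 80% design | 0.4 | 2.07 | 62% | 80% | 37% |
| Planned 80% design | 0.5 | 1.93 | 48% | 80% | 50% |
| Planned 80% design | 0.6 | 1.84 | 37% | 80% | 60% |
| 560 enrolled, 10% attrition | 0.5 | 1.93 | 38% | 89% | 61% |
| One-sided 0.05, sized for 80% | 0.5 | 1.49 | 39% | 80% | 57% |
| One-sided 0.05, drift kept at 2.80 | 0.5 | 1.49 | 31% | 88% | 67% |

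**Same limit, planning effect assumed for the remaining data**

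Stop if Z_t <= (1.96 - 2.80 × (1 - t) - 0.842 × √(1 - t)) / √t, which at t = 0.5 is -0.05. Stopping probability is 2.1% if the planned effect is true and 48% under no effect; power is 79.7%. At t = 0.4 and 0.6 power is 79.9% and 79.6%.

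**The case against.** The formula and the arithmetic are not in dispute. The case for a milder reading has five parts.

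- **The 50% figure belongs to 400 analysed participants, while 560 will be enrolled.** This is fair as a statement of size: for the enrolment target the fall is from about 89% to 61%. But section 11.3 offers the extra participants as a cushion against attrition, slow sites and a larger intracluster correlation, not to pay for the interim rule. A loss of 28 points remains.
- **The rule only recommends, and an independent monitoring board oversees the trial.** The loss does occur only if the recommendation is followed. Still, this is the protocol's formal rule, and one that is safe only when ignored needs correcting.
- **An information fraction of 0.4 is speculative.** The protocol fixes no fraction. Some 6-month data may be available at the look, and beta1 in the model of section 11.6 is the 3-month contrast. The main result therefore uses 0.5, and 0.4 is only one end of a range.
- **The 0.29 is a standardised mean difference at 6 months, while beta1 is a log-link coefficient.** True, but the rule can be applied to the Z statistic through the planning drift of 2.80, without converting 0.29 to a log-link coefficient.
- **The planned effect is not the only reasonable choice.** Conditional power under the observed trend would stop at Z <= 0.965 and leave 74.1% power. That is workable but costs about 6 points. Conditioning on the null is what cannot be defended here.

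**Conclusion.** The concern holds. As written, section 11.9 recommends stopping for futility unless the interim result is already close to two-sided significance. Under the protocol's planned effect, with t = 0.5 and a final critical value of 1.96, following the rule reduces power from 80% to about 50%. For 560 enrolled with 10% attrition, the fall is from about 89% to 61%.

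The result rests on three assumptions: the information fraction, the usual independent-increments approximation for conditional power, and the recommendation being followed. The fraction and the sidedness change the size but not the conclusion. Power under the rule ranges from 37% to 60% as t goes from 0.4 to 0.6 in the 80% design, and is 57% to 67% with a one-sided 0.05 test at t = 0.5. This must be corrected before the interim analysis.

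**What to change.** In section 11.9, replace P(0) by the probability that the final test rejects in favour of REMAS, given the interim data and the planning effect behind 0.29. Apply it on the Z scale with the planning drift of 2.80. Recommend stopping only if this probability is 0.2 or less.

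State the information fraction assumed, the final critical value and sidedness, and that the rule is non-binding. Report the power cost with those assumptions: under 1 percentage point for t from 0.4 to 0.6, both at drift 2.80 and at the drift of 3.17 expected from 560 enrolled.

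The cost is one paragraph of protocol wording, with no added participants, visits or data collection.
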